15.2. SECONDARY EFFICACY

The secondary efficacy analyses will be performed for the FAS and PPAS. Descriptive statistics will be presented by treatment arm for all secondary efficacy variables for each measurement timepoint, including mean, SD, minimum, maximum, median, quartiles and 95% CI for the mean for continuous variables. Number and percentage of subjects and the 95% CI for the percentage will be calculated for categorical variables. Descriptive statistics for change from baseline will also be determined where

Document: \ieedc-vnasc01\BIOSdata\Abivax\ABX464\FZA92720\Biostatistics\Documentation\SAP\ABX464-103_SAP_V2.0_10MAY2021

Author: [REDACTED]

Version Number: 2.0
Version Date: 10May2021

Template No.: CS_TP_BS016 Revision 5

Reference: CS_WI_BS005

Effective Date: 01Apr2018

relevant and is defined in Section 6.6.

15.2.1. SECONDARY EFFICACY VARIABLES & DERIVATIONS

15.2.1.1. Number and Percentage of Patients in Clinical Remission at Week 8 and Week 16

Clinical remission is defined as:

- A stool frequency subscore = 0 or 1
- A rectal bleeding sub-score = 0
- An endoscopy sub-score = 0 or 1 (modified to exclude friability)

This endpoint will be calculated per treatment arm and presented descriptively.

Percentage of patients in clinical remission at Week 8

$$= \frac{\text{Number of patients in treatment arm with clinical remission at Week 8}}{\text{Total number of patients in the treatment arm}} \times 100$$

Percentage of patients in clinical remission at Week 16

$$= \frac{\text{Number of patients in treatment arm with clinical remission at Week 16}}{\text{Total number of patients in the treatment arm at Week 16}} \times 100$$

Percentage of patients in clinical remission at Week 8 or Week 16

$$= \frac{\text{Number of patients in treatment arm with clinical remission at Week 8 or Week 16}}{\text{Total number of patients in the treatment arm at Week 8 or Week 16}} \times 100$$

Number of patients with clinical remission at week8 and not at week 16 as well as number of patients with clinical Remission at Week 16 and not at Week 8 will also be presented.

Document: \\ieddc-vnasc01\BIOSdata\Abivax\ABX464\FZA92720\Biostatistics\Documentation\SAP\ABX464-103_SAP_V2.0_10MAY2021

Author: [REDACTED]

Version Number: 2.0
Version Date: 10May2021

Template No.: CS_TP_BS016 Revision 5

Reference: CS_WI_BS005

Effective Date: 01Apr2018

15.2.1.2. Combined Number and Percentage of Patients in Clinical Remission at Week 8 and Week 16

Clinical remission is defined in Section 15.2.1.1. The number and percentage of patients in clinical remission at both Week 8 and Week 16 will be summarized by treatment arm.

Percentage of patients in clinical remission at Week 8 and Week 16

$$= \frac{\text{Number of patients in treatment arm with clinical remission at Week 8 and Week 16}}{\text{Total number of patients in the treatment arm at both visits}} \times 100$$

15.2.1.3. Number and Percentage of Patients with Clinical Response at Week 8 and Week 16

Clinical response is defined as

- A reduction from baseline in MMS ≥ 2 points, and
- A reduction in MMS $\geq 30\%$ from baseline with a decrease in rectal bleeding sub-score ≥ 1 point or absolute rectal bleeding sub-score ≤ 1 point

This endpoint will be summarized by treatment arm.

Percentage of patients with clinical response at Week 8 and Week 16

$$= \frac{\text{Number of patients in treatment arm with clinical remission at Week 8 and Week 16}}{\text{Total number of patients in the treatment arm}} \times 100$$

Number of patients with clinical response at week8 and not at week 16 as well as number of patients with clinical response at Week 16 and not at Week 8 will also be presented.

Document: \\ieedc-vnasc01\BIOSdata\Abivax\ABX464\FZA92720\Biostatistics\Documentation\SAP\ABX464-103_SAP_V2.0_10MAY2021

Author: [REDACTED]

Version Number: 2.0
Version Date: 10May2021

Template No.: CS_TP_BS016 Revision 5

Reference: CS_WI_BS005

Effective Date: 01Apr2018

15.2.1.4. Number and Percentage of Patients with Endoscopic Improvement and Remission, by Segment at Week 8 and Week 16

Endoscopic improvement is defined as an endoscopic sub-score ≤ 1 and endoscopic remission is defined as an endoscopic sub-score = 0. The improvement and remission will be summarized by segment (descending colon, sigmoid colon, rectum) as well as overall endoscopic improvement and remission for Week 8 and Week 16.

Percentage of patients with endoscopic improvement (or remission) at Week 8 for segment X

$$= \frac{\text{Number of patients in treatment arm with endoscopic improvement (or remission) at Week 8 in segment X}}{\text{Total number of patients in the treatment arm for segment X at Week 8}} \times 100$$

The percentage of patients with endoscopic improvement or remission at Week 16 for segment X will be calculated similarly for data available at Week 16.

The overall percentage of patients with endoscopic improvement or remission at Week 8 will be calculated as follows:

Percentage of patients with endoscopic improvement (or remission) at Week 8 =

$$= \frac{\text{Number of patients in treatment arm with endoscopic improvement (or remission) at Week 8}}{\text{Total number of patients in the treatment arm at Week 8}} \times 100$$

The overall percentage of patients with endoscopic improvement or remission at Week 16 will be calculated similarly for data available at Week 16.

Number of patients with endoscopic improvement and endoscopic remission, by segment at week8 and not at week 16 as well as number of patients with endoscopic improvement and endoscopic remission, by segment at Week 16 and not at Week 8 will also be presented.

Document: \\ieddc-vnasc01\BIOSdata\Abivax\ABX464\FZA92720\Biostatistics\Documentation\SAP\ABX464-103_SAP_V2.0_10MAY2021

Author: [REDACTED] Version Number: 2.0
Version Date: 10May2021

Template No.: CS_TP_BS016 Revision 5

Reference: CS_WI_BS005

Effective Date: 01Apr2018

15.2.1.5. Number and Percentage of Patients with Mucosal Healing at Week 8 and Week 16

Mucosal healing is defined as both endoscopic remission and histological remission (Geboes score < 2.0)

A patient is said to be in Histological Remission, if severity of Geboes score component (APPENDIX 4) grades (2A, 2B, 3, 4 & 5) are zero with non-missing grades (0 and 1).

Numerical Geboes Score is the sum of all the components (Grades: 0-Architectural changes, 1-Chronic inflammatory infiltrate, 2A-Eosinophils in lamina propria, 2B- Neutrophils in lamina propria, 3- Neutrophils in epithelium, 4-Crypt destruction and 5-Erosions and ulcerations).

Descriptive Statistics and MMRM are based on Numerical Geboes score. Geboes score is based on rectal biopsy only.

Percentage of patients with mucosal healing at Week 8 (or Week 16) =

$$\frac{\text{Number of patients in treatment arm with mucosal healing at Week 8 (or Week 16)}}{\text{Total number of patients in the treatment arm at Week 8 (or Week 16)}} \times 100$$

Number of patients with mucosal healing at week8 and not at week 16 as well as number of patients with mucosal healing at Week 16 and not at Week 8 will also be presented.

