2.4. Secondary Endpoints

The secondary endpoints of this study are:

- Number and rate of patients in clinical remission at Week 8, per each intervention/treatment group. Clinical remission, based on the Mayo Scoring system, is defined as stool frequency subscore = 0 or 1 and rectal bleeding subscore = 0 and endoscopy subscore = 0 or 1 (modified to exclude friability).

- Combined number and rate of patients in clinical remission at Week 8 and at Week 16, per each intervention/treatment group.
- Number and rate of patients with clinical response at Week 8 and Week 16 per intervention/treatment group. Clinical Response is defined as a reduction in Mayo Score of at least 2 points and greater than or equal to 30 percent from baseline with an accompanying decrease in rectal bleeding sub-score of greater than or equal to 1 point or absolute rectal bleeding sub-score of less than or equal to 1 point.
- Number and rate of patients with endoscopic improvement, by segment, and number and rate of patients with endoscopic remission, by segment, at Week 8 and at Week 16 (if available) per intervention/treatment group. Endoscopic improvement is defined as a Mayo endoscopic sub score of ≤1 (excluding friability) and endoscopic remission defined as sub score of 0.
- Number and rate of patients with mucosal healing. Mucosal healing is defined as both endoscopic remission and histological remission (Geboes score < 2.0).
- Reduction relative to baseline in stool and rectal bleeding frequency at every study visit by ABX464 dose group and versus placebo.
- Reduction relative to baseline in partial Modified Mayo Score at every study visit and Modified Mayo Score at Week 16 (if available) by ABX464 dose group and versus placebo.
- Reduction relative to baseline in fecal calprotectin and CRP levels at Week 8 and Week 16 by intervention/treatment group.
- Change relative to baseline in miRNA-124 expression in rectal/sigmoidal biopsies at Week 8 and Week 16 (if available) and in total blood at every timepoints by intervention/treatment group.
- The scores and changes from baseline in IBDQ at Week 8 and Week 16 per intervention treatment group.
- Reduction relative to baseline of infiltrate/histopathology (rectal/sigmoidal biopsies) using the Robarts Histopathology Index (RHI), the Geboes and Nancy Histology Scoring Scales at Week 8 and Week 16 (if available) per intervention/treatment group.

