3.1.1. Design and methodology

This phase IIb study will evaluate the efficacy and the safety of 3 dose-levels of ABX464, administered daily in improving Modified Mayo Score (MMS) in patients with moderate to severe Ulcerative Colitis at Week 8.

Eligible patients will be randomized into 4 parallel intervention/treatment groups:

Intervention/treatment Active Arm	
Group #1: 25mg qd	1 capsule of 25mg ABX464 + 1 capsule of Placebo
Group #2: 50mg qd	1 capsule of 50mg ABX464 + 1 capsule of Placebo
Group #3: 100mg qd	2 capsules of 50mg ABX464
Group #4: Placebo	2 capsules of Placebo

The study design is presented below:

At Week 16, regardless of their clinical/symptomatic response and the actual treatment/dose received, patients willing to continue the study treatment and eligible for enrollment will roll over in an Open Label Extension study (ABX464-104). In this extension study, all patients will be dosed with ABX464 50mg QD. ABX464-104 is a separate clinical protocol subject to health authorities and ethics committee approvals.

In the present induction study (ABX464-103), randomization will be stratified according to the following factors:

- 1) US versus non-US patients
- 2) patients without previous exposure to biological or JAK inhibitors versus patients with previous exposure to biological drugs or JAK inhibitors.

The proportion of patients with previous exposure to biologics or JAK inhibitors will be limited to 60%, including a maximal proportion of patients with previous treatment with vedolizumab of 20%. The maximal proportion of patients with previous exposure with JAK inhibitors will be limited to 10%.

Patients will be treated for 16 Weeks in this induction study. All endoscopies (videos) will be centrally reviewed. E-Diaries will be used to collect frequency of stools, rectal bleedings, number of capsules taken and the intake time.

From Day 1 onwards, randomized patients will be seen at the investigational site on a regular basis (cf. flow-chart).

Flexible sigmoidoscopy with rectal and sigmoidal (if the sigmoidal is inflamed) biopsies will be performed at screening, at Day 57 +/- 4 days (week 8) and at Day 113 +/- 4 days (week 16). The Day 113 measurement will only be taken if patient does not experience endoscopic improvement at Day 57 (i.e.:

endoscopy sub-score of 2 or 3).

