5.2.4. Day 57 and Day 113 Visits

- IBD Questionnaire (as the first visit procedure);
- Physical examination and vital signs;
- Body weight;
- At Day 113, population Pharmacokinetics blood samples at either pre-dose, 1, 2, 4h and if possible 48 h (Day 115 only) or pre-dose, 0.5, 1.5, 3h and if possible 48 (Day 115 only);
- Hematology and Biochemistry including blood pregnancy test for all women of childbearing potential, coagulation parameters and troponin;
- Blood sample for miR-124 dosage (PAXgene® tube) and cytokines determination;
- 12-leads ECG;
- Fecal calprotectin;
- Sigmoidoscopy with rectal/sigmoidal biopsies (Day 113 endoscopy is conditional on the response at Day 57);
- Modified Mayo Score at Day 57 (and Day 113 if available; OR pMMS at Day 113 if Day113 endoscopy not performed);
- Check treatment compliance;
- Adverse Events reporting;
- Study treatment dispensation at Day 57 visit;
- Review the patient e-Diary;
- At Day 113, enrolment of patients willing to take part to the maintenance phase;
- Schedule next patient visits.

5.2.5. End of Study Visit (Within a week after last dose \pm 2 days)

This EoS visit applies to all premature discontinued patients and to patients not taking part to the maintenance study. Patients will perform an End of Study Visit (EoS) within a Week after last dosing (i.e D120 \pm 2 days if the patient completed the study and is not taking part in maintenance study). Patients will be treated according to the standard of care from the last day of study treatment.

Following examinations/procedures should be performed:

- Physical examination and vital signs;
- Body weight;
- Hematology and Biochemistry and a follow-up 3 Weeks later;
- Partial Modified Mayo Score;
- 12 leads ECG;
- Fecal calprotectin;
- Adverse Events reporting.

NB#1: In case of premature discontinuation occurring during the treatment phase (D1-D113), the above examinations should be performed as an End of Study Visit 7 days \pm 2 days after last dose.

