2.2. SECONDARY OBJECTIVES

The secondary objectives are:

- To evaluate the effect of the different dose groups of ABX464 versus placebo on:
 - MMS at Week 16 (if available) and on partial Modified Mayo Score (pMMS) at every study visit
 - Clinical remission at Week 8 and at Week 16 (if available)
 - Clinical response at Week 8 and at Week 16 (if available)

Document: \\ieedc-vnasc01\BIOSdata\Abivax\ABX464\FZA92720\Biostatistics\Documentation\SAP\ABX464-103_SAP_V2.0_10MAY2021

Author: [REDACTED]

Version Number: 2.0
Version Date: 10May2021

Template No.: CS_TP_BS016 Revision 5

Reference: CS_WI_BS005

Effective Date: 01Apr2018

- Endoscopic improvement and endoscopic remission, by segment, at Week 8 and Week 16 (if available)
- Mucosal healing at Week 8 and Week 16 (if available)
- Stool and rectal bleeding frequency at every study visit
- Fecal calprotectin and C-reactive Protein (CRP) levels at Week 8 and Week 16
- miR-124 expression in tissue (Ribonucleic Acid (RNA) later) at Week 8 and Week 16 (if available) and in total blood at every timepoint
- Rectal/sigmoidal infiltrates using the Robarts Histopathology Index (RHI), the Geboes and Nancy Histology Scoring Scales at Week 8 and Week 16 (if available)
- Quality of Life (QoL) measured by the Inflammatory Bowel Disease Questionnaire (IBDQ) at Week 8 and Week 16
- IL-6, TNF α , IL-1b, IL-10 plasma concentrations at every timepoint
- To evaluate the global effect of ABX464 on MMS at Week 8 and Week 16 (if available) and on pMMS at every study visit versus placebo
- To assess the pharmacokinetics of ABX464 and its main active metabolite ABX464-N_Glu after oral administration of different daily doses of ABX464 using population approach
- To evaluate the safety profile of the different dose groups of ABX464 versus placebo.

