2.3. ESTIMANDS

The primary and secondary estimands to support regulatory decisions are described in Table A below. The intercurrent event is the early discontinuation of patients from the study and/or missing Week 8 efficacy assessments.

Table A List of Estimands

Document: \\ieddc-vnasc01\BIOSdata\Abivax\ABX464\FZA92720\Biostatistics\Documentation\SAP\ABX464-103_SAP_V2.0_10MAY2021

Author: [REDACTED]

Version Number: 2.0
Version Date: 10May2021

Template No.: CS_TP_BS016 Revision 5

Reference: CS_WI_BS005

Effective Date: 01Apr2018

Estimand	Definition	Attributes			
		Population	Variable/Endpoint	Intercurrent event handling strategy	Population-level summary measure
Primary	Optimal ABX464 dose	All patients randomized, received at least one dose of study drug and provided at least one efficacy data point	Mean change in MMS from baseline to Week 8	Missing Week 8 MMS components (stool frequency, rectal bleeding and endoscopy subscores) will be imputed using methods detailed in section 7.3.	Mean change from baseline
Secondary	The effect of different dose groups vs placebo on secondary variables	All patients randomized, received at least one dose of study drug and provided at least one efficacy data point	Mean change from baseline to Weeks 8 and 16 in pMMS	Missing Week 8 pMMS components (stool frequency and rectal bleeding subscores) will be imputed using methods detailed in section 7.3.	Mean change from baseline
			Clinical remission or response at Weeks 8 and 16	Patients with missing Week 8 assessment will be considered non-responders	Proportion of responders in each treatment group
			Mean change from baseline to Week 8 in fecal calprotectin and CRP levels	Missing fecal calprotectin and CRP values will not be imputed.	Mean change from baseline

Document: \\ieddc-vnasc01\BIOSdata\Abivax\ABX464\FZA92720\Biostatistics\Documentation\SAP\ABX464-103_SAP_V2.0_10MAY2021

Author: [REDACTED]

Version Number: 2.0
 Version Date: 10May2021

Template No.: CS_TP_BS016 Revision 5

Reference: CS_WI_BS005

Effective Date: 01Apr2018

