Flexible sigmoidoscopy with rectal and/or sigmoidal biopsies will be performed at screening, at Day 57 +/- 4 days (Week 8) and at Day 113 +/- 4 days (Week 16). The Day 113 measurement will only be taken if the patient does not experience endoscopic improvement (i.e. endoscopy sub-score of 2 or 3) at Day 57. In the event of clinical progression of the disease after Week 8, defined as at least a 2-point increase from screening in pMMS, with a MMS ≥ 4 confirmed by an endoscopy sub score of 2 points or higher, the patient will exit the study.

Study Design

Document: \\ieedc-vnasc01\BIOSdata\Abivax\ABX464\FZA92720\Biostatistics\Documentation\SAP\ABX464-103_SAP_V2.0_10MAY2021

Author: [REDACTED]

Version Number: 2.0
Version Date: 10May2021

Template No.: CS_TP_BS016 Revision 5

Reference: CS_WI_BS005

Effective Date: 01Apr2018

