15.2.3. ANALYSIS OF SECONDARY EFFICACY VARIABLES

15.2.3.1. Analysis of Secondary Variables at Week 8 and at Week 16

In addition to the descriptive statistics as described in Section 15.2 and specific subsections of Section 15.2. ANCOVA models, using the same procedure as described for the primary efficacy analysis in section 15.1.3, will be used to make the assessments listed below:

- Global effect of ABX464 treatment vs placebo in change from baseline in MMS at Week 8
- Combined number and percentage of patients in clinical remission at Week 8 and Week 16
- The number and percentage of patients with clinical response at Week 8 and Week 16
- The number and percentage of patients with endoscopic improvement and remission, by segment at Week 8 and Week 16
- Proportion of patients with mucosal healing at Week 8 and Week 16
- Daily stool frequency and number of patients with reduction relative to baseline in stool frequency sub-score at every study visit
- Number of patients with reduction relative to baseline in rectal bleeding sub-score at each visit
- Frequencies and percentages for rectal bleeding and stool frequency sub-score categories
- Frequencies and percentages for Mucosal Appearance at endoscopy by segment
- Total IBDQ scores and change from baseline at Week 8 and Week 16

In addition, the above variables will be included in a listing by patient. The frequency of daily stools and categories of rectal bleeding as recorded in the e-Diary will be listed for the duration of the study.

[REDACTED]

[REDACTED]

[REDACTED]

Document: \\ieddc-vnasc01\BIOSdata\Abivax\ABX464\FZA92720\Biostatistics\Documentation\SAP\ABX464-103_SAP_V2.0_10MAY2021

Author: [REDACTED]

Version Number: 2.0
Version Date: 10May2021

Template No.: CS_TP_BS016 Revision 5

Reference: CS_WI_BS005

Effective Date: 01Apr2018

15.2.3.2. Analysis of Number and Percentage of Patients in Clinical Remission at Week 8

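### Clinical remission at both Week 8 and Week 16 is 0% on schedule in every arm, because the Day 113 endoscopy is reserved for Week 8 endoscopic non-improvers

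*SAP*

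**What the plan says.** **Endpoint.** Protocol 2.4 lists: "Combined number and rate of patients in clinical remission at Week 8 and at Week 16, per each intervention/treatment group". It carries no availability qualifier, although the remission objective in Protocol 2.2 and SAP 2.2 does. SAP 15.2.1.2 fixes the meaning: "The number and percentage of patients in clinical remission at both Week 8 and Week 16 will be summarized by treatment arm". Its denominator is the arm's patients at both visits, with no further definition. SAP 15.2.3.1 includes "Combined number and percentage of patients in clinical remission at Week 8 and Week 16" among the assessments to be made with ANCOVA models.

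**Definition.** Remission requires stool frequency 0 or 1, rectal bleeding 0 and endoscopy 0 or 1 (Protocol 2.4, SAP 15.2.1.1). Endoscopic improvement uses the same endoscopy cut (SAP 15.2.1.4).

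**Schedule.** Protocol 3.1.1: "The Day 113 measurement will only be taken if patient does not experience endoscopic improvement at Day 57", where lack of improvement means a sub-score of 2 or 3. SAP 3.1 agrees: "The Day 113 measurement will only be taken if the patient does not experience endoscopic improvement". For everyone else Protocol 5.2.4 provides "OR pMMS at Day 113 if Day113 endoscopy not performed".

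**Missing data.** For remission and response at Weeks 8 and 16, Table A in SAP 2.3 says only "Patients with missing Week 8 assessment will be considered non-responders". The imputation rules in SAP 7.3 are written for Week 8, and SAP 15.2.2 sends the reader back to 7.3.

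**Related summaries.** SAP 15.2.1.1 also plans a rate for remission at Week 8 or Week 16. SAP 15.2.1.1 and 15.2.1.3 to 15.2.1.5 plan counts of patients with a status at Week 8 and not at Week 16, and the reverse.

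**The concern.** The endpoint asks for an endoscopic fact at Week 16 in exactly the patients whom the schedule does not re-examine endoscopically. If the plan is followed, the report will show 0% in every arm. A reader could take that for failure to sustain remission, when it only reflects who was scoped.

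The same feature reaches other Week 16 results. A Week 8 remitter without a Day 113 endoscopy can appear as having lost remission. Two programmers could choose different Week 16 denominators and both comply with the text.

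**Working it through.** The plan gives no expected value for this endpoint, so there is no figure to reproduce. The sample size concerns the Week 8 primary endpoint and does not bear on the point.

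**1. The zero.** Each sub-score runs from 0 to 3, so one visit has 4 × 4 × 4 = 64 combinations and two visits have 64 × 64 = 4,096.
- Week 8 remission: 2 × 1 × 2 = 4 combinations, times 64 at Week 16 = 256. All have Week 8 endoscopy 0 or 1.
- Observable Week 16 remission: Week 8 endoscopy 2 or 3 gives 4 × 4 × 2 = 32 combinations, times 4 = 128.
- Both: none, because the two sets need different Week 8 endoscopy scores.

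The outcome is then constant, and ANCOVA has no variance to model.

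**2. Routes around it.**
- Missing Week 8 data: the patient is a non-responder at Week 8 (SAP 7.3, 15.1.2) and cannot qualify.
- End of Study visit: Protocol 5.2.5 lists no sigmoidoscopy.
- Endoscopy confirming progression (Protocol 3.1.1, 7.2): Protocol 3.1.1 needs pMMS at least 2 above screening. An eligible screening MMS of 5 or more implies pMMS of at least 5 − 3 = 2, hence at least 4 at progression. Under the original protocol (MMS 4) the figure is at least 3. Remission allows at most 1.
- An off-schedule endoscopy at Day 113, for instance after a local read that differs from the central one, could give isolated counts. These would be departures from the schedule.

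**3. What is known without a Week 16 endoscopy.** For remission, endoscopy decides only 2 of the 16 stool-by-bleeding combinations: (0,0) and (1,0). Stool above 1 or bleeding above 0 is known non-remission. These are counts of combinations, not of patients.

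For response (SAP 15.2.1.3), check the bleeding criterion first; failing it means known non-response. Otherwise the required MMS drop is max(2, 0.3 × baseline) in whole points, which leaves a ceiling T. Unknown endoscopy adds 0 to 3, so pMMS ≤ T − 3 meets the MMS part and pMMS > T fails it.

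| Baseline MMS | Drop | T | Undetermined pMMS |
|---|---|---|---|
| 4 (original protocol) | 2 | 2 | 0–2 |
| 5 | 2 | 3 | 1–3 |
| 6 | 2 | 4 | 2–4 |
| 7 | 3 | 4 | 2–4 |
| 8 | 3 | 5 | 3–5 |
| 9 | 3 | 6 | 4–5 |

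At baseline 9 a pMMS of 6 is excluded. It means bleeding 3, which is neither 1 or less nor a decrease.

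Mucosal healing requires endoscopic remission, so no Week 8 healer has a scheduled Week 16 endoscopy. All un-scoped patients are undetermined for endoscopy and mucosal healing.

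**4. Denominators.** Week 16 remission and mucosal healing divide by the arm's patients at Week 16 (SAP 15.2.1.1, 15.2.1.5). SAP 7 allows either the analysis set or subjects with data. Response divides by all patients in the arm (15.2.1.3), and endoscopic rates by those with Week 16 data (15.2.1.4). Those two are stated.

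**5. Response formula.** In SAP 15.2.1.3 the numerator counts clinical remission at Week 8 and Week 16. Programmed literally, it repeats the structural zero.

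**6. Illustration only.** Inputs: Phase IIa Week 8 rates (Protocol 1.3), namely endoscopic improvement 50.0% on ABX464 and 11.1% on placebo, and remission 35.0% and 11.1%; 61 per arm; and an assumed 20% Week 16 remission among re-scoped patients in both arms.
- Un-scoped counted as failures: 0.500 × 0.20 = 10.0% against 0.889 × 0.20 = 17.8%, a difference of −7.8 points.
- Re-scoped patients only: 20% against 20%, a difference of 0.
- With 10% or 30% assumed, the first becomes −3.9 or −11.7; the second stays 0.
- Week 8 remitters not re-scoped: 61 × 0.350 = 21.4 and 61 × 0.111 = 6.8.

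**The case against.** The SAP already plans the Week 8 or Week 16 rate and both discordant counts, presents remission descriptively, and acknowledges in its objectives that Week 16 data may be unavailable. The protocol's word combined might even mean either visit. This limits the consequences, but the availability remark does not say how an un-scoped patient is classified. The SAP defines the endpoint as both visits and lists the either-visit rate separately, and the protocol synopsis underlines the word joining the two visits.

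Several stronger readings that a reader might infer are not supported:
- *All Week 16 denominators are undefined.* Those for response and endoscopy are stated.
- *The SAP has no Week 16 rule at all.* Some lines after the list in 15.2.3.1 are redacted. One can say only that no visible text gives a rule.
- *Week 16 endoscopic data come only from Week 8 non-improvers.* That holds for scheduled endoscopies. An endoscopy confirming progression, mapped to the next visit under SAP 6.3, could add a Week 8 improver.
- *Every Week 8 improver is unclassifiable at Week 16.* Symptom scores settle many cases for remission and response.
- *The drug will look worse than placebo at Week 16.* The −7.8 arises only if un-scoped patients count as failures. It is the assumed 20% times the difference in improvement rates, and the 0 restates the equal-rates assumption. The Phase IIa placebo group had 9 patients.

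The response numerator is plainly a slip, since the surrounding text says response. It still needs correcting because it is the formula to be programmed.

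**Conclusion.** The point holds. Clinical remission at both visits is 0% on schedule in every arm, by definition and schedule alone. It cannot show durability or support a comparison between arms. The Week 8 and not Week 16 counts for remission, endoscopy and mucosal healing mix true losses with patients never re-scoped. Week 16 endoscopic rates describe, on schedule, a subgroup selected after randomisation by Week 8 non-improvement, so they do not compare all randomised patients. The denominators for both-visits remission, Week 16 remission and Week 16 mucosal healing remain open.

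A reader might infer that the trial's main conclusion is at risk. It is not: the primary analysis uses Week 8 MMS, and the ordered dose tests rest on it. The defect is in secondary results and should be fixed before unblinding. The Phase IIa figures show only that an unstated denominator can matter; the conclusion does not rest on them.

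**What to change.** Before unblinding, and recorded in SAP 3.3:

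1. Declare the both-visits remission rate not estimable under the endoscopy schedule and remove it from the 15.2.3.1 list. Report the planned Week 8 or Week 16 rate over all FAS patients. State that it does not measure durability, and that Week 8 endoscopic improvers who were not remitters cannot convert without a further endoscopy.
2. State the Week 16 denominators for remission and mucosal healing. Label endoscopy-based Week 16 results as covering patients with a Week 16 endoscopy (on schedule, Week 8 endoscopic non-improvers), descriptive only.
3. In the Week 8 and not Week 16 tables, show three groups: known loss; undetermined because not re-scoped by design; and discontinued or no Week 16 data. For remission, stool above 1 or bleeding above 0 is a known loss. For response, apply the bleeding criterion and then the limits tabulated above.
4. Correct the response numerator to clinical response and report Week 8 and Week 16 separately.

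Optionally, a labelled sensitivity analysis could carry the Week 8 endoscopy sub-score forward for patients not re-scoped by design and combine it with their observed Week 16 stool and bleeding scores. It cannot show endoscopic relapse.

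The cost is SAP text and programming, with no extra endoscopies. The price is that durability of remission stays unestimated and the either-visit rate answers a different question.
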